Study Design: international multicenter prospective observational cohort study.

For the primary outcome PRBC will be evaluated as total amount during the ECMO run and for the first 28 days as daily amount. The total amount of PRBC, adjusted for the ECMO length of stay, will be evaluated in light of pre-ECMO parameters (age, comorbidities, postoperative state and severity scores) and of daily data (bleeding episodes, ECMO blood flow, dieresis, CRRT, Hb, major events). Daily occurrence of PRBC transfusion will be described according to pre-ECMO characteristics and daily parameters (Hb, bleeding, hemodynamics, renal function, circuit change).

Plasma, platelets, Fibrinogen, Antithrombin III administration will be evaluated according to pre-ECMO data and according to daily APTT level (or other coagulation monitoring adopted), bleeding episodes, sepsis.

For the secondary outcomes type of anticoagulant will be described as well as daily dose and daily target for the parameter targeted (APTT, ACT, r-TEG, anti-Xa according to local protocol). Anticoagulation will be described in relation to pre-ECMO parameters and daily episodes of bleeding and occurrence of sepsis.

Bleeding episodes will be described according to site (airway – including tracheotomy - oro-nasal, gastric, intrathoracic, abdominal, intestinal, retroperitoneal, urinary tract, other) and classified according to severity following 5 adjusted categories of the Bleeding Academic Research Consortium (BARC) score: Type 0, no bleeding; Type 1, Any overt bleeding that requires heparin infusion rate reduction or PRBC transfusion (provided Hb drop was related to bleeding); Type 2, any overt bleeding that requires heparin infusion rate reduction and packed red blood cells transfusion or non-surgical procedure to stop bleeding (provided Hb drop was related to bleeding); Type 3, Any life-threatening bleeding that required PRBC transfusion and surgical intervention for control of bleeding or ECMO discontinuation; Type 4: any fatal bleeding.

The study is prospective and, consequently, in each center all consecutive adult patients who are eligible according to inclusion and exclusion criteria should be included in the study up to 20 patients.

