1. Clinical data

- Demographics: age, gender, weight, height, BMI
- Pre-existing pulmonary disease: asthma, cystic fibrosis, chronic obstructive pulmonary disease, pulmonary hypertension, pulmonary fibrosis, chronic restrictive lung disease
- Main co-morbidities: diabetes mellitus, chronic renal failure, ischemic heart disease, heart failure, chronic liver failure, neurological impairment
- Cause of ARF: bacterial pneumonia, viral pneumonia, trauma/burns, aspiration pneumonia, pancreatitis, pulmonary vasculitis, post lung transplantation
- Diagnosis: ARDS, Chronic end stage respiratory disease
- Postoperative period < 7 days. Pregnancy or peri-partum.
- Pre-ECMO hospital/ICU length of stay, mechanical ventilation days
- Patient characteristics at ICU admission: SAPS 2, SOFA score, PaO₂/FiO₂ ratio, hematocrit, platelets
- ECMO severity scores: PRESERVE score, RESP Score, ECMOnet if appropriate

2. ECMO and daily management data

- Type of circuit: heparin-bonded or not, type of oxygenator
- Type of anticoagulation: heparin, bivalirudin, argatroban, no anticoagulant

- Dose of anticoagulation
- Amount of PRBC, Plasma, platelets transfused (unit and ml) the day before
- Eventual Fibrinogen administration (mg)
- Antithrombin III level
- Antithrombin III administration (Type: human plasma-derived, recombinant) and dosage
- Episodes of bleeding classified according to site (airway – including tracheotomy - oro-nasal, gastric, intrathoracic, abdominal, intestinal, retroperitoneal, urinary tract, other) and severity according to 5 adjusted categories of the Bleeding Academic Research Consortium (BARC) score: Type 0, no bleeding; Type 1, Any overt bleeding that requires heparin infusion rate reduction or PRBC transfusion (provided Hb drop was related to bleeding); Type 2, any overt bleeding that requires heparin infusion rate reduction and packed red blood cells transfusion or non-surgical procedure to stop bleeding (provided Hb drop was related to bleeding); Type 3, Any life-threatening bleeding that required PRBC transfusion and surgical intervention for control of bleeding or ECMO discontinuation; Type 4: any fatal bleeding
- Daily blood and air flow, ECMO FiO₂
- 24 hours diuresis and fluid balance
- Use of continuous renal replacement therapy
- Mean arterial pressure, use of vasopressors
- Septic shock
- Hemoglobin, hematocrit, platelet count, fibrinogen if available.
- Daily gas exchange: pH, PaO₂, PaCO₂, SaO₂

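### A heparin cut is part of how bleeding is graded, and dose is described against bleeding with no time order, so the comparison is biased toward lower dose on bleeding days

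*Combined protocol and SAP*

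**What the plan says.** The Study Design section sets out the secondary outcomes. For anticoagulation, "type of anticoagulant will be described as well as daily dose and daily target for the parameter targeted", and then: "Anticoagulation will be described in relation to pre-ECMO parameters and daily episodes of bleeding and occurrence of sepsis".

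The same section grades bleeding, and Patient data Collection (2. ECMO and daily management data) repeats the grading:

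- The lowest grade of actual bleeding is worded: "Type 1, Any overt bleeding that requires heparin infusion rate reduction or PRBC transfusion (provided Hb drop was related to bleeding".
- For the second grade, a heparin cut is paired with red-cell transfusion, and a procedure short of surgery is given as a further route.
- The third grade has no heparin criterion: "Any life-threatening bleeding that required PRBC transfusion and surgical intervention for control of bleeding or ECMO discontinuation".
- The fourth grade covers fatal bleeds and likewise has no heparin criterion.

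The daily data list has the item "Dose of anticoagulation" and the item "Type of anticoagulation: heparin, bivalirudin, argatroban, no anticoagulant". Data collection methods puts anticoagulation on a 24-hour collection cycle. Blood products in the daily list are recorded for the preceding day; the dose and bleeding items carry no such offset. Statistical Analysis plans mean dose with a 95% confidence interval and says nothing about which dose belongs with which bleed.

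**The concern.** One side of the comparison is partly defined by a fall in the other. Where an overt bleed reaches Type 1 because heparin was turned down, the lower dose is the reason the day is counted. An overt bleed with no dose change, no transfusion and no procedure has no clear category, so bleeds in which the dose was left alone are less likely to be counted.

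With one dose per 24 hours and no stated time order, the natural pairing is that day's dose with that day's bleed. The result then mixes the dose the patient was on when the bleed began with the clinicians' response to it. The Background attributes complications partly to anticoagulant use, and the Rationale promises to read transfusion in light of anticoagulation and bleeding. Many readers will therefore take a dose-by-bleeding table as evidence on whether more intense anticoagulation precedes bleeding. On that question the table would be biased downward.

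**Working it through.** **No figure to reproduce.** The plan gives no sample size calculation, effect size or expected bleeding rate for this point. The check is a reading of the definitions, followed by an illustration whose inputs are all assumptions.

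**Where the loop applies**

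| Bleed or patient | Heparin cut in the definition? |
|---|---|
| Type 1 | Yes, sufficient; PRBC transfusion is the alternative |
| Type 2 | Yes, paired with PRBC; a non-surgical procedure is a further route, depending on how the and/or is grouped |
| Types 3 and 4 | No |
| Bivalirudin, argatroban or no anticoagulant | No; the criterion names heparin only |

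**Formula.** Let Δpre be the mean pre-bleed dose on counted bleeding days minus the mean dose on other days. Let Dpre be the mean pre-bleed dose on counted bleeding days, s the share of those days with a heparin cut, r the fractional cut and f the fraction of the day it lasts. If the cut does not depend on the dose, the same-day difference is

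Δsame = Δpre − s·r·f·Dpre.

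The second term is never positive in its effect on Δsame, and it is zero only if no counted bleed involves a cut.

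**Illustration A (4,000,000 simulated patient-days).** Assumed: dose index mean 100, SD 30; overt bleeding on about 10% of days; PRBC or a procedure in 40% of overt bleeds, independent of the cut; heparin cut in a fraction q of overt bleeds; f = 0.5. A bleed counts if either response occurred, so s = q / (q + 0.4 − 0.4q). Odds ratios (OR) are per SD of pre-bleed dose.

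Hand check with no true effect: for q = 0.3, s = 0.3/0.58 = 0.52 and Δsame = −0.3/0.58 × 0.5 × 0.5 × 100 = −12.9. For q = 0.6, s = 0.6/0.76 = 0.79 and Δsame = −19.7. Both match the simulation.

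| q | r | s | OR 1.0 | OR 1.2 | OR 1.5 | OR 2.0 |
|---|---|---|---|---|---|---|
| 0 | – | 0 | 0 | +5 | +11 | +18 |
| 0.3 | 0.5 | 0.52 | −13 | −8 | −3 | +3 |
| 0.6 | 0.5 | 0.79 | −20 | −15 | −10 | −4 |
| 0.6 | 1 | 0.79 | −39 | −36 | −32 | −27 |
| 0.9 | 1 | 0.96 | −48 | −45 | −41 | −37 |
| Pre-bleed dose, any q | | | 0 | +5 | +11 to +12 | +18 to +20 |

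The pre-bleed contrast recovers the right sign in every column. So does the same-day contrast when restricted to bleeds that qualified through PRBC or a procedure with no cut (about 0, +5, +11 to +12, +18 to +20), given the assumed independence.

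**Illustration B (milder inputs).** Assumed: dose mean 15, SD 4; bleeding on 8% of days; OR 1.3 per SD of the previous day's dose; day-to-day dose correlation 0.8. The lagged contrast is about +1.0, so the same-day contrast before any cut is about 0.8 × 1.0 = +0.8, and mean dose on bleeding days is about 15.8.

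- 25% cut, half the day, half of bleeds: 0.8 − 0.5 × 0.25 × 0.5 × 15.8 = about −0.2.
- Same cut in 30% of bleeds: 0.8 − 0.3 × 0.25 × 0.5 × 15.8 = about +0.2.
- 25% cut, whole day, every bleed: 0.8 − 0.25 × 15.8 = about −3.2.
- 50% cut, whole day, every bleed: 0.8 − 0.50 × 15.8 = about −7.1.

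All four lie below the lagged +1.0. Whether they fall below zero depends on how often, how deeply and for how long heparin is cut.

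**The case against.** The strongest reply is that the plan never promises to estimate whether anticoagulation precedes bleeding. The Aim of the study is to describe the type, trigger and level of anticoagulation in practice. Anticoagulation is the thing described, and bleeding and sepsis are the circumstances. If the question is how clinicians dose when a patient bleeds, the same-day dose is the right quantity. This stands: same-day dose is a legitimate description of management, provided it is labelled as such. Nor does the loop bias the stand-alone endpoints, namely anticoagulant type and dose, and bleeding by site and severity. What remains is that the plan does not say which question the joint description answers, and as written the table cannot separate the two.

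Three stronger readings are tempting, and the documents do not support them.

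- *Bleeding will necessarily appear linked to lower anticoagulation.* PRBC transfusion alone gives Type 1, Types 3 and 4 have no heparin criterion, and patients not on heparin fall outside the wording. The same-day pairing is itself an inference from the daily items, since the text leaves timing open. Positive same-day contrasts remain in some of the settings above.
- *Lower APTT would look harmful by definition.* No bleeding type is defined by APTT or any other monitoring value. These could be affected only indirectly, if sampled after a dose change, and the sampling time is not stated.
- *The dose is undated.* Collection is every 24 hours, so the day is known; what is missing is the order of dose and bleed within it.

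**Conclusion.** The concern holds in a limited form. For heparin patients, the daily dose–bleeding description is biased toward lower dose on bleeding days whenever some bleeds qualify through a heparin cut, and nothing in the plan removes that bias. The direction follows from the definitions once dose and bleeding are paired within the day.

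The size does not follow from the documents. With no true effect, Illustration A gives −13 to −48 on an index of 100 across the cut settings tried. At OR 1.5 per SD, a pre-bleed difference of about +11 becomes −3 or −10 with a 50% half-day cut in 30% or 60% of overt bleeds. At OR 2.0 with the cut in 30%, it stays at +3. These figures rest wholly on assumed bleeding rates, cut frequency, depth and duration, and on cuts being independent of dose and of transfusion. They show that reversal is possible, not that it will occur.

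Because the analysis is descriptive, the harm lies in interpretation. The change is nonetheless worth making before analysis: it is cheap and gives a less biased answer to the question readers will ask.

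**What to change.** In Study Design (secondary outcomes) and Statistical Analysis:

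1. Relate the onset of a bleed on day t to anticoagulant dose and monitoring value on day t−1, or to the last value before onset where available. Restrict this to days on which the patient was free of bleeding at t−1, within the period of daily recording.
2. Report same-day dose separately, labelled as management after bleeding.
3. Where the qualifying route of each bleed is recorded, add a sensitivity analysis limited to bleeds that qualify without a heparin cut. State how the and/or in Type 2 is grouped, since this decides which bleeds enter it.
4. Optionally, record overt bleeding yes/no regardless of the response. This is not in the listed data and would need one added form field.

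**Cost.** Items 1 and 2 need plan wording and a lagged variable from data already collected. The first ECMO day drops out of the lagged analysis. Days 15–28 drop out as well if recording there is weekly. Study Design and Study duration make weeks three and four weekly, while Data collection methods has ECMO management data daily for 28 days and anticoagulation every 24 hours. These passages must be reconciled before the span of the lagged analysis can be fixed.

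### The adjusted BARC bleeding scale is not exhaustive: some overt, non-life-threatening bleeds meet none of Types 0 to 4

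*Combined protocol and SAP*

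**What the plan says.** The Study Design section says that bleeding is recorded by site and "classified according to severity following 5 adjusted categories of the Bleeding Academic Research Consortium (BARC) score". The types are:

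- The two lowest grades are worded "Type 0, no bleeding; Type 1, Any overt bleeding that requires heparin infusion rate reduction or PRBC transfusion (provided Hb drop was related to bleeding").
- The next grade up, Type 2, is worded "any overt bleeding that requires heparin infusion rate reduction and packed red blood cells transfusion or non-surgical procedure to stop bleeding", with the same proviso about the haemoglobin drop.
- The grade above that, Type 3, is worded "Any life-threatening bleeding that required PRBC transfusion and surgical intervention for control of bleeding or ECMO discontinuation".
- The highest grade is worded "Type 4: any fatal bleeding".

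Patient data Collection, item 2 (ECMO and daily management data), repeats the scale as a daily data item: "severity according to 5 adjusted categories of the Bleeding Academic Research Consortium (BARC) score: Type 0, no bleeding; Type 1, Any overt bleeding", and so on through Type 4. It adds no category and no default rule.

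The grade has two uses. Bleeding by site and severity is an end point of the secondary aim (Summary; Aim of the study). Study Design also says "Plasma, platelets, Fibrinogen, Antithrombin III administration will be evaluated according to pre-ECMO data and according to daily APTT level", and the same sentence goes on to name bleeding episodes and sepsis as further factors.

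**The concern.** A severity scale that is meant to classify every episode needs a place for each one. Here Type 0 means that no bleeding occurred, while Type 1 already requires one of two specific responses. Platelets, plasma and fibrinogen appear in no type. Surgery appears only in Type 3, which is confined to life-threatening bleeding.

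Two stated outputs are exposed. The first is the incidence and severity of bleeding, which the expected results promise to describe worldwide. The second is the evaluation of plasma, platelet and fibrinogen use against bleeding, because some bleeds treated with only those products have no type.

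The plan makes such cases plausible. It lists no anticoagulant as an option, and for those patients Type 1 can be reached only through PRBC. It keeps patients who refuse transfusion, although they are analysed separately. It also cites a survey that found strong variation between centers in blood product use. When the grade depends on treatment, the same bleed may be graded at one center and not at another.

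A bleed that is not captured as bleeding at data entry cannot be restored in the analysis.

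**Working it through.** The plan gives no figure to reproduce, and no sample-size or power formula applies. The check is one of logical coverage.

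**Inputs.** These are the type definitions in Study Design, confirmed against Patient data Collection, item 2. A non-fatal overt bleed is described by seven yes/no facts: heparin reduction (H), PRBC (R), non-surgical procedure (N), surgery (S), ECMO discontinuation (D), platelets/plasma/fibrinogen (P) and life-threatening (L). That gives 2^7 = 128 combinations, of which 64 are not life-threatening. The haemoglobin proviso is taken as met, which favours the plan.

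**Rules.** Type 1 is H or R. The and/or wording of Type 2 allows two readings and that of Type 3 allows three:

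- Type 2: (H and R) or N; alternatively H and (R or N).
- Type 3: L and R and (S or D); alternatively (L and R and S) or D; alternatively L and ((R and S) or D).

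**Result.** A combination is ungraded if it meets none of Types 1 to 3. Type 0 is ruled out because bleeding is present, and Type 4 because it is not fatal.

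| Type 2 reading | Type 3 reading | Ungraded if | Ungraded of 128 | Of the 64 not life-threatening |
|---|---|---|---|---|
| (H and R) or N | L and R and (S or D) | no H, R, N | 2^4 = 16 | 8 |
| (H and R) or N | (L and R and S) or D | no H, R, N, D | 2^3 = 8 | 4 |
| (H and R) or N | L and ((R and S) or D) | no H, R, N; not both L and D | 2^2 × 3 = 12 | 8 |
| H and (R or N) | L and R and (S or D) | no H, R | 2^5 = 32 | 16 |
| H and (R or N) | (L and R and S) or D | no H, R, D | 2^4 = 16 | 8 |
| H and (R or N) | L and ((R and S) or D) | no H, R; not both L and D | 2^3 × 3 = 24 | 16 |

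The second row is the reading most favourable to the plan. Its four ungraded non-life-threatening combinations have H = R = N = D = 0 with S and P free:

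- no treatment
- platelets, plasma or fibrinogen only
- surgery only
- surgery plus those products

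All four are also ungraded in every other row, so the gap does not depend on how the and/or wording is read.

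**Boundary.** A non-life-threatening surgical bleed with heparin reduction or PRBC does get a grade. If only one of the two was given and there was no non-surgical procedure or ECMO discontinuation, that grade is Type 1. The surgical gap is therefore limited to surgery with neither.

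These are counts of logical combinations, not expected proportions of patients.

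**The case against.** The strongest case on the other side has five parts.

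- **The products are evaluated against bleeding episodes, not grades.** Site is recorded separately and includes an option for other sites, and cannulation-site bleeding has its own line. An ungraded bleed could still be recorded by site. This stands. A reader might infer that every bleed treated only with these products drops out of the comparison, but the documents do not support that. Such a bleed is lost only if the site enters Type 0 or records nothing.
- **Site behaviour is unknown.** A reader might infer that sites are forced either to enter Type 0 or to guess. CRF completion instructions are not in the documents, and leaving the grade blank is a third possibility. This also stands.
- **The threshold may be deliberate.** The first listed aim refers to major bleeding, and leaving merely observed bleeds ungraded would fit that. This stands only in part. No such threshold is stated, Type 0 is labelled as absence of bleeding, the expected results promise bleeding incidence in general, and a bleed that needs surgery is not plainly minor.
- **A product infusion could count as a non-surgical procedure.** The text does not say so, and that reading could put a platelet-only bleed in Type 2, above a PRBC-only bleed in Type 1. This does not stand.
- **Other fields could recover the link.** The item 3 fields for reason for transfusion and presence of bleeding are listed for PRBC only, so for the other products the daily bleeding item is the main listed link. With no indication field, it is also inference to say that product use would look prophylactic.

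**Conclusion.** The scale is not exhaustive, and nothing else in the document closes the gap. The bleeds affected are overt, non-fatal and not life-threatening, and were only observed, treated only with platelets, plasma or fibrinogen, or controlled by surgery with neither heparin reduction nor PRBC. Incidence and severity could partly reflect local coding, and the evaluation of those three products against bleeding could miss some bleeds treated with them.

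The size cannot be estimated. A reader might try a share such as 10% to 30% of overt bleeds, but the documents give no bleeding frequency to support any figure. Incidence would be too low by such a share only if episodes were counted and every such bleed were coded Type 0 or omitted. In a per-patient count, anyone who also has a graded bleed still counts, so the shortfall would be smaller.

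The recorded amounts of blood products, which are the primary-aim end points, are not changed. The conclusion rests on the literal type definitions and on no completion rule outside the document settling these cases. The change should be made: the defect lies in a stated data-collection rule, and correcting it costs little.

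**What to change.** Change Study Design and Patient data Collection, item 2, together:

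1. Record overt bleeding yes/no as its own item, separate from the grade.
2. Add a separate residual category for overt bleeding that meets none of Types 1 to 4, and keep Type 1 as it is. Widening Type 1 to take these bleeds would mix trivial bleeding with bleeding that needed PRBC and would weaken the severity end point.
3. State which type a non-life-threatening bleed controlled by surgery receives.
4. Tick the treatments given for each bleed: none, anticoagulant change, PRBC, platelets, plasma, fibrinogen, procedure, surgery, other.
5. Use overt bleeding yes/no alongside the grade in the plasma, platelet and fibrinogen analyses, so that severity information is kept.

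The cost is one more category, one yes/no field, one tick-list and the rewording of two sections. More minor bleeds will be recorded. The change affects measurement only, not patient care.

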Moreover, most of the available data on transfusions during ECMO are heterogeneous, usually including VV-ECMO and veno-arterial-ECMO (VA-ECMO) configuration, and mixing adults with neonatal and pediatric cohorts, which are historically more represented. Recently, a meta-analysis including 1042 patients presenting refractory ARDS and focusing on complication rate and hospital mortality associated with VV-ECMO showed a limited impact of bleeding and total number of haemo-derivates administrated on patient outcome. [32]

In this context, the decision of giving a transfusion during ECMO support is still a real challenge since several parameters have to be taken into account at the same time. A strict trigger has not yet been defined in this population, and the literature on critically ill patients suggests a relevant reduction in the amount of transfusion.

Rationale for the study

Providing adequate DO₂ can be approached in several ways during vv-ECMO support, but the hemoglobin target is always a critical point, and a relevant piece of the puzzle of assuring the best oxygenation in patients affected with acute respiratory failure (ARF). There may be important variations between hospitals and countries in the use of PRBC transfusions, which may impact patient outcome. Large scale, national, and international studies are currently lacking.

While there are extensive reviews on predicted ECMO survival, and management (even with many debated issues), there is a significant knowledge gap in understanding the benefits and risks of transfusion during VV-ECMO. [30, 33, 34]

An international multicenter study will evaluate prospective observational data of transfusion practices during VV-ECMO for ARF, analyzing it in light of anticoagulation and bleeding episodes.

Aim of the study

The PROTECMO study is aimed at being a collaborative study including a large number of ECMO centers worldwide, describing, in real practice,

- 1) Incidence of major bleeding events and amount of blood product transfused
- 2) Type, trigger and level of anticoagulation adopted

The descriptive variable end points for the primary aim will be the daily and the total amount of PRBC and other blood products (Plasma, Platelets, Fibrinogen, Antithrombin III).

The descriptive variable end points for the secondary aim will be the type and dose of anticoagulation, and episodes of bleeding according to site and severity.

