ECMO management data will be collected daily for the first 28 days. Additionally, fluid balance, adverse events, Hb and all hematological data, anticoagulation management and monitoring will be collected every 24 hours.

Data will also be collected for the duration of mechanical ventilation, duration of ECMO, and ICU length of stay. Clinical outcome assessment will be made, with date of death, ICU discharge, hospital discharge, sixth month mortality.

Statistical Analysis

Descriptive statistics including frequency (percentage), median and interquartile range (IQR) will describe overall population and groups of survivors and non-survivors.

In order to describe current transfusion practice the amount of PRBC, Plasma and Platelets, will be described as units and ml and as a number of transfusions adjusted for ECMO length of stay and considering the concomitant bleeding episodes.

Fibrinogen and Antithrombin III will be described as mg or units respectively and as a number of administration.

Anticoagulation will be reported as type, mean dosage and the confidence interval (CI 95%).

Hb average level and the confidence interval (CI 95%) will be reported.

Baseline categorical and continuous variables will be compared for transfusion and ECMO weaning groups. In particular categorical variables will be compared with chi-square tests and continuous variables will be compared with Student's T-test, or Wilcoxon rank-sum tests, otherwise.

Multiple COX regression analysis will be used in order to explore the impact of confounding factors such as baseline patient severity, ECMO length of stay, bleeding episodes and possible others covariates and factors that will be observed and raised relevance during the first exploratory or univariate analysis. The impact of relevant confounding factors such as length of ECMO run, pre-ECMO severity scores, pre-ECMO administration of transfusions will be analyzed separately and together in multiple analyses.

In particular daily RBC transfusion will be studied according to the association to renal function, fluid balance, worst Hb level, episodes of bleeding, use of vasopressors, ECMO blood flow.

A p-value less of than 0.05 will be considered significant. Data handling and analyses will be done with SAS 9.4 software (SAS Institute Inc, Cary, NC, USA) and R 3.3 software (R Foundation for Statistical Computing).

Patient data Collection

For each included patient the investigators will collect the following data:

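### Bleeding Types 1 and 2 count only a reduction of heparin, so the same non-life-threatening bleed gets a different grade, or none, on bivalirudin or argatroban

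*Combined protocol and SAP*

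**What the plan says.** Study Design in the combined protocol and SAP sets out five bleeding levels. The lowest is "Type 0, no bleeding". The next is "Type 1, Any overt bleeding that requires heparin infusion rate reduction or PRBC transfusion (provided Hb drop was related to bleeding". Above it comes "Type 2, any overt bleeding that requires heparin infusion rate reduction and packed red blood cells transfusion or non-surgical procedure to stop bleeding", which ends with the same Hb-drop proviso. Type 3 needs a life-threatening bleed and Type 4 a fatal one, and neither mentions an anticoagulant.

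Patient data Collection, item 2 (ECMO and daily management data), repeats these definitions with heparin as the only drug named. The same list contains "Type of anticoagulation: heparin, bivalirudin, argatroban, no anticoagulant".

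Aim of the study names "episodes of bleeding according to site and severity" as a secondary end point, alongside the type and dose of anticoagulation. Study Design adds: "Anticoagulation will be described in relation to pre-ECMO parameters and daily episodes of bleeding and occurrence of sepsis". No section says that reducing an agent other than heparin counts towards Type 1 or Type 2.

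**The concern.** A severity grade should reflect the bleed and the care it required. Here it also reflects which drug was running. Two patients can have the same overt bleed and the same response (the anticoagulant is turned down, with or without PRBC) and still be graded differently, because one was on heparin and the other on argatroban. One of them may have no grade at all: Type 0 excludes anyone who bled, and Types 3 and 4 need a life-threatening or fatal event.

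The study exists to describe practice, and bleeding severity is one of its stated end points. A drug-dependent scale puts an artefact into that description which more patients will not remove. Any table of severity by anticoagulant would carry it most directly.

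**Working it through.** The plan gives no figure on this point to reproduce. The check is to apply the written rules to every care pattern.

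**Inputs.** The definitions of Types 0 to 2 in Study Design, applied to a non-life-threatening overt bleed. R = anticoagulant reduced, P = bleeding-related PRBC, N = non-surgical procedure. R counts only if the drug is heparin. Type 1 is R or P when Type 2 is not met. The and/or in Type 2 is not bracketed, so there are two readings:

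- Reading A: (R and P) or N.
- Reading B: R and (P or N).

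| Care given | A: heparin | A: other agent | B: heparin | B: other agent |
|---|---|---|---|---|
| R only | 1 | none | 1 | none |
| R + P | 2 | 1 | 2 | 1 |
| R + N | 2 | 2 | 2 | none |
| R + P + N | 2 | 2 | 2 | 1 |
| P only | 1 | 1 | 1 | 1 |
| N only | 2 | 2 | none | none |
| P + N | 2 | 2 | 1 | 1 |
| None of these | none | none | none | none |

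**Result.** The grade depends on the drug in 2 of 8 patterns under Reading A and in 4 of 8 under Reading B. All of them include a reduction. If R counts for any anticoagulant, 0 of 8 differ under either reading.

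**Hb-drop proviso.** It closes Types 1 and 2 and could attach to PRBC alone or to the whole criterion. The table assumes PRBC alone. If it governs everything, a reduction without a bleeding-related Hb drop is ungraded on heparin too, and the differences remain only for bleeds with such a drop.

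**Illustration on assumed rates (none from the documents).** Per non-life-threatening overt bleed, take R = 50% (range 30% to 70%), P = 40% and N = 10%, independent and the same on every drug. Under Reading A, with the proviso on PRBC alone, moving from heparin to another agent has these effects:

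- Type 2 becomes Type 1: 0.5 × 0.4 × 0.9 = 18% (10.8% to 25.2%).
- Type 1 becomes no grade: 0.5 × 0.6 × 0.9 = 27% (16.2% to 37.8%).
- Total regraded or lost: 45% (27% to 63%). Under Reading B it equals R: 50% (30% to 70%).
- If the proviso governs the whole criterion (Reading A), the 18% stays, since counted PRBC already implies the Hb drop. The 27% shrinks, so the total lies between 18% and 45%.

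On the same inputs Type 2 is 1 − (1 − 0.5 × 0.4) × 0.9 = 28% of such bleeds on heparin and 10% on another agent. Pooled over the cohort, with 10% of bleeds on other agents, it is 0.9 × 28% + 0.1 × 10% = 26.2%. With 50% it is 19%.

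**Direction.** For a single bleed the grade can only fall or vanish. The share of Type 2 among graded non-life-threatening bleeds can move either way:

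- R and P independent: 0.28/0.73 = 38% on heparin against 0.10/0.46 = 22%.
- R and P never together: 0.10/0.91 = 11% on heparin against 0.10/0.46 = 22%.

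**The case against.** The strongest reply is that no comparison of grades between anticoagulants is expressly planned. Study Design relates anticoagulation to daily bleeding episodes without saying whether the grade is used, and the group comparisons in Statistical Analysis are by survival, transfusion and ECMO weaning. This stands. A reader might infer that the plan contains a biased between-drug analysis, and the documents do not support that. What remains is the severity end point itself, which pools bleeds graded by different rules. In the pooled figures the effect may be small if few patients are on other agents.

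A second reply is that sites will read heparin as any anticoagulant. Some may, but nothing tells them to, and mixed readings would add inconsistency between centers.

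A third is that the data allow regrading, since "adverse events, Hb and all hematological data, anticoagulation management and monitoring will be collected every 24 hours" and drug, dose and PRBC amounts are listed. This is only partly true. A lower dose does not show that the bleed was the reason, and no listed item records the reason. Study Design and Study duration also describe weekly recording in the third and fourth weeks, whereas Data collection methods describes daily collection for 28 days.

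Fourth, some overt bleeds have no grade on heparin either. That is correct and is a separate gap. In the illustration it accounts for 27 of the 54 percentage points ungraded off heparin (0.6 × 0.9 = 54%). Only the other 27 come from the heparin wording.

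**Conclusion.** The point holds as a defect in the written rule. With a reduction alone, or a reduction plus PRBC, a non-life-threatening overt bleed is graded by drug under both readings of Type 2. Under Reading B, bleeds managed with a reduction and a non-surgical procedure are affected too. If the Hb-drop proviso governs the whole criterion, the point is confined to bleeds with a bleeding-related Hb drop. The wording gap is certain; its size and its direction in a reported severity distribution are not. The documents give neither the share of patients on other agents nor any bleeding rate, so the percentages above are illustrations only.

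Stronger conclusions that a reader might draw are not supported:

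- That 45% of bleeds off heparin drop one level. On those assumptions 18% drop a level, and 27% leave the scale.
- That severity always looks milder off heparin. The Type 2 share among graded bleeds can reverse.
- That the primary end point is affected. PRBC amount is measured without the grade. Statistical Analysis says "daily RBC transfusion will be studied according to the association to renal function, fluid balance, worst Hb level, episodes of bleeding", but not whether the grade enters.
- That the incidence of major bleeding is wrong. The plan does not tie that term to any of the types, and Types 3 and 4 do not depend on the drug.

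The study is exploratory, so the risk is a misleading description of practice and not a failed test. The change should still be made, because the reason for a reduction is hard to recover afterwards.

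**What to change.** In Study Design and in item 2 of Patient data Collection, replace the heparin-specific term in Types 1 and 2 with *reduction or interruption of any anticoagulant*. In the same edit, bracket the and/or in Type 2 so that one reading remains, and state whether the Hb-drop proviso applies to PRBC only or to the whole criterion.

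Add one CRF item, completed on bleeding days: was the anticoagulant reduced or stopped because of this bleed (yes/no)?

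Note in the analysis text that patients on no anticoagulant cannot meet a reduction criterion, so their Type 1 and Type 2 grades are not directly comparable with those of anticoagulated patients.

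The cost is one extra field per bleeding day, in a study that reports no financial support, and a definition slightly further from a score that the protocol has already adjusted. These are changes to measurement wording only and do not affect care.
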